10.2.2 Secondary Efficacy Endpoints

Secondary Efficacy Endpoints include:

- Investigator-assessed ORR per RECIST v1.1
- Investigator-assessed ORR per ir-RECIST (immune-related criteria)
- Investigator-assessed DOR per RECIST v1.1 and ir-RECIST
- Investigator-assessed PFS per RECIST v1.1 and ir-RECIST
- PRO
- Safety

OS was defined as the interval from the date of enrollment in the first treatment phase to the date of death from any cause or censored to the last follow up for patients alive. OS will be assessed with the Kaplan-Meier method and median (95% CI) time will be calculated. ORR was defined as the proportion of patients who achieved an objective response (CR or PR). DoR was defined as the time from the date of first documented response to the date of PD or death from any cause, whichever occurred first; time was censoredat the date of last follow up for patients alive and without PD. DOR will be assessed with the Kaplan-Meier method and median (95% CI) time will be calculated.

10.3 Overall response rate and Duration of Response as Determined by Investigator per RECIST v1.1 and Ir-RECIST

For the first endpoint (ORR), objective response is defined as a confirmed CR or PR as determined by the investigators per RECIST v1.1 (see Appendix III). Patients not meeting these criteria, including patients without at least one post-baseline response assessment, will be considered non-responders. For the second endpoint (ORRmod), ir-RECIST responses, which incorporate measurement of new lesions and confirmation by repeat assessment performed ≥ 28 days after the first criteria for response are first met, are described in detail in Appendix II. For the analysis according to ir-RECIST, patients not meeting these criteria, including patients without at least one post-baseline response assessment, will be considered non-responders.

DOR will be analyzed for the subset of *objective response-evaluable* patients who achieved an objective response as assessed by the investigator per RECIST v1.1 and Ir-RECIST. The DOR is defined as the time from the initial occurrence of documented CR or PR (whichever occurs first) until documented disease progression as determined by the investigator or death due to any cause, whichever occurs first.

DOR will be estimated using the Kaplan-Meier method. The 95% CIs for median duration of objective response will be computed using the Brookmeyer and Crowley method. *Patients who have not progressed or who have died at time of analysis will be censored at the last tumor assessment date.*

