3.5 Outcome Measures

3.5.1 Efficacy Outcome Measures

The efficacy outcome measures for this study are as follows:

- Investigator-assessed PFS according to RECIST v1.1
- Investigator-assessed PFS according to ir-RECISTThe

secondary efficacy outcome measures are as follows:

- Investigator assessed response rate per RECIST v1.1 or death from any cause on study
- Investigator assessed response rate per ir-RECIST or death from any cause on study
- Investigator assessed DOR per RECIST v1.1
- Investigator assessed DOR per ir-RECIST
- OS
- Centrally-assessed objective response, DOR, PFS according to RECIST vers 1.1 and ir-RECIST

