10.9 Handling of Missing Data

For objective response (per ir-RECIST or RECIST v1.1), patients without a post-baseline tumor assessment will be considered non-responders.

For DOR, data from patients who did not experience disease progression or died will be included in the analysis as censored observations on the last date that the patient was known to be progression free, defined as the date of the last tumor assessment. If no tumor assessments were performed after the date of the first occurrence of a complete or partial response, duration of objective response will be censored at the date of the first occurrence of a complete or partial response (whichever occurs first) plus 1 day.

For the analysis of PFS, data for patients without disease progression or death will be censored at the date of the last tumor assessment (or, if no tumor assessments were made after the baseline visit, at the date of first

treatment plus 1 day). Data for patients who were lost to follow-up will be censored at the last date of tumor assessment at which the patient was known to be progression free.

For the analysis of OS, patients who are still alive at the time of analysis will be censored at the time of their last study assessment (for active patients) or at the last date known alive (for patients in follow-up).

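### Section 10.3 censors responders who have died, although the protocol defines death from any cause as a duration-of-response event

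*Protocol*

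**What the plan says.** The protocol speaks about the end of DOR in three places.

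- **Section 10.2.2** defines the endpoint: "DoR was defined as the time from the date of first documented response to the date of PD or death from any cause". Its censoring rule is "time was censoredat the date of last follow up for patients alive and without PD".
- **Section 10.3** repeats the definition, with DOR running "until documented disease progression as determined by the investigator or death due to any cause, whichever occurs first". A few lines later, after naming the Kaplan-Meier and Brookmeyer-Crowley methods, it gives its own censoring rule: "Patients who have not progressed or who have died at time of analysis will be censored at the last tumor assessment date".
- **Section 10.9** returns to censoring: "For DOR, data from patients who did not experience disease progression or died will be included in the analysis as censored observations". The censoring date there is the last tumour assessment.

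A related wording problem sits in the outcome lists. Section 3.5.1 gives a secondary outcome as "Investigator assessed response rate per RECIST v1.1 or death from any cause on study". A matching bullet covers ir-RECIST, and the synopsis has the same pair. Sections 10.2.2 and 10.3 define objective response as CR or PR only and treat everyone else as a non-responder.

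**The concern.** The censoring sentence in 10.3 removes an event that the same section has just placed in the endpoint. A programmer who codes from it would take a responder who dies without a progression scan and end that patient's time, event-free, at the last scan. Kaplan-Meier then treats the patient as if the response would have lasted as long as it does in those still under observation. Death is the opposite of that, so the censoring is informative and the estimated DOR is too long.

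DOR is a stated secondary objective. Only 27 patients enter the combination phase, so the DOR analysis will rest on a small number of responders, and the handling of one or two deaths can move the median.

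**Working it through.** The protocol states no DOR figure, so there is none to reproduce. The check has two parts: comparing the texts, then sizing the effect under stated assumptions.

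**1. The rules side by side**

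| Place | Is death a DOR event? | Who is censored | Censoring date |
|---|---|---|---|
| 10.2.2 | Yes | Alive and without PD | Last follow-up |
| 10.3, definition | Yes | – | – |
| 10.3, censoring sentence | No | Not progressed, or dead | Last tumour assessment |
| 10.9 | Unclear | Two readings | Last tumour assessment |

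In the 10.3 censoring sentence the group that has died has its own relative clause, so the negation attached to progression does not carry over to it. As written, it censors deaths.

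In 10.9 the wording can mean patients who had neither progression nor death, which is the usual rule, or patients without progression together with patients who died. It therefore neither confirms nor cures 10.3. The PFS sentence in the same section shows how the authors write the rule when it is clear: "For the analysis of PFS, data for patients without disease progression or death will be censored at the date of the last tumor assessment".

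**2. Size under constant hazards**

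Input: *d*, the share of first DOR events that are deaths without prior progression. The protocol gives no value, so a range is assumed. Let the total event hazard be λ.

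- Deaths as events: median = ln 2 / λ.
- Deaths censored: only the progression hazard (1 − d)λ is estimated, so median = ln 2 / [(1 − d)λ].
- Ratio = 1 / (1 − d).

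| d | 1/(1 − d) | Inflation | Assumed 6-month median becomes |
|---|---|---|---|
| 0.05 | 1.053 | 5% | 6.3 months |
| 0.10 | 1.111 | 11% | 6.7 months |
| 0.20 | 1.250 | 25% | 7.5 months |
| 0.30 | 1.429 | 43% | 8.6 months |

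The formula censors at the death date. It ignores the further step in 10.3 of moving the censoring back to the last scan.

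**3. A small-sample example that includes that step (invented data)**

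Ten responders: progression at 2, 4, 6, 8, 10 and 12 months; deaths without progression at 3, 5 and 7 months, with last scans at 2, 4 and 6 months; one patient ongoing at 14 months.

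- Deaths as events: the survival estimate falls by 0.1 at each of 2, 3, 4, 5 and 6 months and reaches 0.50 at 6. Median 6 months (6.5 under the midpoint convention, since the curve sits at exactly 0.50 until 7).
- Deaths censored at the last scan: 9/10 = 0.900 at 2 months; × 7/8 = 0.788 at 4; × 5/6 = 0.656 at 6; × 3/4 = 0.492 at 8. Median 8 months.

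Here 3 of 9 events are deaths. The formula would give 1/(1 − 1/3) = 1.50, while the example gives 8/6 = 1.33. With so few responders the median moves in jumps, so the example shows direction and not an expected size.

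**The case against.** The best defence is that this is a slip of drafting and not a chosen analysis. The protocol defines death as a DOR event twice, 10.2.2 states the correct censoring group, and PFS counts death as an event in 10.2.1, 10.4 and 10.9. One sentence stands against all of that. DOR carries no hypothesis test or decision rule, and if deaths without progression make up only 5% to 10% of first events the median moves by only 5% to 11%.

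Much of this stands. A slip is the likeliest explanation, and the size is unknown. It does not remove the point, because the 10.3 sentence is the censoring instruction placed directly after the DOR definition, and 10.9 does not overrule it.

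Some stronger readings are tempting, but the documents do not support them:

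- *Section 10.9 repeats the error.* It is ambiguous, and one natural reading is the correct rule.
- *Deaths among responders would be hidden.* Deaths are events for OS (10.5) and PFS (10.2.1, 10.4). Section 10.7 lists and summarises serious events including deaths, and the DMC reviews safety about every three months. Only the DOR estimate would miss them.
- *The response rate would count deaths as responses.* The clause appears only in the outcome lists. The analysis text in 10.2.2 and 10.3 confines ORR to CR or PR, so this is stray wording to correct and not a faulty analysis.

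**Conclusion.** The censoring sentence in 10.3 is wrong as written: it contradicts the DOR definition in 10.2.2 and 10.3 and the censoring rule in 10.2.2, and 10.9 leaves the conflict open. Applied literally it biases DOR upward. The indicative size is a median about 5% to 43% too long if 5% to 30% of first events are deaths without progression. That range rests on constant hazards and on assumed shares.

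The reach is limited to secondary endpoints. The primary 8-month PFS, the sample size of 27 and the rule of at least 4 progression-free patients are untouched. The death clause in the response-rate bullets is a lesser inconsistency. It should be corrected before the DOR and ORR analyses are programmed, but it is no threat to the trial's main conclusion.

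**What to change.** - **Sections 10.3 and 10.9:** state that responders who are alive and without documented progression at the time of analysis are censored for DOR at the last tumour assessment, and that death without prior progression is an event.
- **Section 10.2.2:** replace last follow-up with last tumour assessment as the DOR censoring date, so that all three sections agree. Without this, correcting 10.3 and 10.9 would still leave two dates.
- **Section 3.5.1 and the synopsis:** remove the trailing death clause from both response-rate bullets in each place, so that the outcome lists match the CR-or-PR definition of ORR.

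The cost is three sentences and four bullets. Nothing changes in design, sample size or data collection. Median DOR may come out slightly shorter than under the present 10.3 wording.

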10.4 Progression Free Survival as determined by Investigator per RECIST v1.1 and Ir-RECIST

PFS is defined as the time from the first dose of TMZ to time of disease progression per RECIST v1.1 and Ir-RECIST as determined by the investigator or death due to any cause on study, whichever occurs first. Patients who have not experienced disease progression and are alive at the time of analysis will be censored at the time of the last tumor assessment.

The Kaplan-Meier method will be used to estimate PFS. The 95% CIs for median PFS were computed using the Brookmeyer and Crowley method. *Patients with no post-baseline tumor assessment will be censored at the time of first dose plus 1 day.*

A patient is considered to have disease progression by ir-RECIST if either of the following conditions is met:

- a) Ir-RECIST criteria for progression were met at a tumor assessment and no subsequent tumor assessment was performed
- b) Ir-RECIST criteria for progression were met at a tumor assessment and at the subsequenttumor assessment the criteria for confirmed progression by ir-RECIST were also met

For patients who meet criterion a), the date of progression is the date of the tumor assessment that met the criteria for ir-RECIST. For patients who meet criterion b), the date of progression is the date of the tumor assessment at which the ir-RECIST criteria for progression were first met. Patients who do not meet either of the above criteria are not considered to have had disease progression by ir-RECIST.

Patients who have not experienced disease progression and are alive at the time of analysis will be censored at the time of the last tumor assessment. The Kaplan-Meier method will be used to estimate PFS. The 95% CIs for median PFS will be computed using the Brookmeyer and Crowley method. Patients with no post-baseline tumor assessment will be censored at the time of first dose plus 1 day.

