Patients who discontinue from study treatment for reasons other than disease progression (e.g., toxicity) will continue scheduled tumor assessments until disease progression, withdrawal of consent or death, whichever comes first. Patients who start a new anti-cancer therapy in the absence of disease progression should be followed according to the protocol schedule until there is confirmed disease progression, withdrawal of consent or death, whichever occurs first.

CD-ROM copies of the CT scans performed at baseline and during treatment until disease progression according to RECIST v1.1 and ir-RECIST criteria will be collected at the Coordinating Center (s.c. Oncologia Medica 1, Fondazione IRCCS Istituto Nazionale dei Tumori) for central review.

The sample of archived tumor tissues used for molecular screening, as well as blood and plasma samples, will be collected for exploratory biomarker assessments.

Patients will undergo an optional tumor biopsy sample collection, if clinically feasible as assessed by investigators, prior to C3D1 of the second treatment phase and/or at the evidence of radiographic disease progression causing treatment discontinuation. These data will be analyzed for the association between changes in tumor tissue and clinical outcome and to understand further the potential mechanisms of resistance to study treatment. A separate informed consent will be signed for optional biopsies requested by the study.

Longitudinal plasma samples (liquid biopsy and PBMCs) will be collected at baseline and every 4-week until best response according to ir-RECIST; after that, these samples (liquid biopsy and PBMCs) will be collected every 8 +/-1 weeks for the first 12 months and every 12 weeks thereafter and at disease progressionleading to treatment discontinuation.

Safety assessments will include the incidence, nature, and severity of adverse events, changes in vital signs and laboratory abnormalities graded per National Cancer Institute Common Terminology Criteria for Adverse Events (NCI CTCAE), Version 4.0.

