Stable Disease (SD): Neither sufficient shrinkage to qualify for PR nor sufficient increase to qualify for PD, taking as reference the smallest sum of the diameters while on study.

Progressive Disease (PD): At least a 20% increase in the sum of diameters of all target and all new measurable lesions, taking as reference the smallest sum on study (*nadir SlD*; this includes the baseline sumif that is the smallest on study). In addition to the relative increase of 20%, the sum must also demonstrate an absolute increase of at least 5 mm.

Impact of New Lesions on Ir-RECIST

New lesions alone do not qualify as progressive disease. However, their contribution to total tumor burden is included in the sum of the diameters, which is used to determine the overall ir-RECIST tumor response.

EVALUATION OF BEST OVERALL RESPONSE USING IR-RECIST:

TIMEPOINT RESPONSE

It is assumed that at each protocol-specified timepoint, a response assessment occurs. Table 11 provides a summary of the overall response status calculation at each timepoint for patients who have measurable disease at baseline.

MISSING ASSESSMENTS AND NOT EVALUABLE DESIGNATION

When no imaging/measurement is done at all at a particular timepoint, the patient is not evaluable (NE) at that timepoint. If only a subset of lesion measurements are made at an assessment, usually the case is also

considered NE at that timepoint, unless a convincing argument can be made that the contribution of the individual missing lesion(s) would not change the assigned timepoint response. This would be most likely to happen in the case of PD. For example, if a patient had a baseline sum of 50 mm with three measured lesions and at follow-up only two lesions were assessed but those gave a sum of 80 mm, the patient will have achieved PD status, regardless of the contribution of the missing lesion.

Table 11 Ir-RECIST Timepoint Response Definitions

Target Lesion	Non-	New	New	Overall Ir-
Definition	Target	Measurable	Unmeasurable	RECIST
	Lesion	Lesions	Lesions	Timepoint
	Definition			Response
CR	CR	No	No	CR
CR	Non-CR or not	No	No	PR
	all evaluated			
PR	Any	Yes or no	Yes or no	PR
SD	Any	Yes or no	Yes or no	SD
Not evaluated	Any	Yes or no	Yes or no	NE
PD	Any	Yes or no	Yes or no	PD
	•			

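### Section 10.4's ir-RECIST rule lets a performed but non-evaluable scan cancel or postpone a documented progression that would count as an event had no scan been done

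*Protocol*

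**What the plan says.** Section 10.4 defines PFS under RECIST v1.1 and ir-RECIST, ending at progression "as determined by the investigator or death due to any cause on study, whichever occurs first". For ir-RECIST it adds two routes by which a progression counts. Under a), "Ir-RECIST criteria for progression were met at a tumor assessment and no subsequent tumor assessment was performed". Under b), the progression criteria were met and, at the next assessment, "the criteria for confirmed progression by ir-RECIST were also met". In both cases the event is dated to the scan that first met the criteria. The section then closes the list: "Patients who do not meet either of the above criteria are not considered to have had disease progression by ir-RECIST". Patients who have not progressed and "are alive at the time of analysis will be censored at the time of the last tumor assessment".

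Appendix II describes two ways for a timepoint to be non-evaluable. One involves no scan: "When no imaging/measurement is done at all at a particular timepoint, the patient is not evaluable (NE) at that timepoint". The other involves a scan that was done: "If only a subset of lesion measurements are made at an assessment", the timepoint is usually non-evaluable too, unless it can be argued that the missing lesions would not change the result.

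Section 10.2.2 lists ir-RECIST PFS among the secondary efficacy endpoints. Section 10.2.1 defines the primary endpoint separately, from the first objective documentation of progression, with no confirmation step.

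**The concern.** The two routes do not cover every case. Route a) asks whether a later assessment was performed, and route b) asks whether it confirmed. Neither asks whether it could be read. A scan that was performed but is non-evaluable closes route a) without opening route b), so the closing sentence applies and the progression disappears.

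The result is incoherent. When confirming information is absent because no scan was done, 10.4 lets the progression stand. When it is equally absent because the scan was uninformative, 10.4 removes it. Section 3.4.4 gives the purpose of ir-RECIST as allowing an apparent increase to be checked at a later assessment, because immune infiltration can mimic growth. A scan that cannot be evaluated is no evidence of that.

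At stake is the secondary ir-RECIST PFS. In an affected patient the error lengthens PFS and never shortens it.

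**Working it through.** The plan gives no figure for this rule, so there is none to reproduce. The check is to apply the rule to scan sequences.

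**Can a scan be performed and yet be non-evaluable?** Yes. Besides partial measurement in Appendix II, Appendix III covers poor image quality, an obstructed view, and a contrast contraindication that arises after baseline. Appendix II says RECIST v1.1 conventions apply where it does not state otherwise.

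**Does another section close the gap?** Section 10.9 censors PFS at the last tumor assessment without requiring it to be evaluable. For patients lost to follow-up it uses the last assessment at which they were known to be progression-free, which is the sounder principle, but this does not alter routes a) and b). Appendix II says progression may be confirmed at 4 weeks or more, and does not say what a non-evaluable scan does.

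**Sequences.** Assumptions: scans at weeks 8, 16, 24, 32 and 40, an illustrative grid based on the 8-week interval in Section 3.1.1; patient alive; route b) met if the next scan again shows progression. Eight months is 8 × 30.4375 / 7 = 34.8 weeks. SD = stable, PD = progression criteria met, NE = performed but non-evaluable.

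| Scans (week) | 10.4 read literally | NE scans skipped |
|---|---|---|
| SD 8, SD 16, PD 24, no later scan | event 24 | event 24 |
| SD 8, SD 16, PD 24, PD 32 | event 24 | event 24 |
| SD 8, SD 16, PD 24, SD 32, SD 40 | censored 40 | censored 40 |
| SD 8, SD 16, PD 24, NE 32 | censored 32 | event 24 |
| SD 8, SD 16, PD 24, NE 32, PD 40 | event 40 | event 24 |
| SD 8, PD 16, NE 24, PD 32 | event 32 | event 16 |
| SD 8, SD 16, SD 24, PD 32, NE 40 | censored 40 | event 32 |

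- Rows 1 and 4 show the inconsistency: adding one unreadable scan turns an event at week 24 into censoring at week 32.
- Dropped events gain 32 − 24 = 8 weeks (row 4) or 40 − 32 = 8 weeks (row 7) of progression-free follow-up.
- Re-dated events move by 40 − 24 = 16 weeks (row 5) or 32 − 16 = 16 weeks (row 6).
- At week 34.8, rows 5 and 7 change from progressed to progression-free. Row 4 is censored before that date, so it leaves the Kaplan-Meier risk set and is not an 8-month success. Row 6 is an event before 8 months either way.
- Row 3 is the same under both readings. A progression that a readable scan does not confirm is set aside, as ir-RECIST intends.

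**The case against.** **Partial scans are often still progression.** Appendix II says the exception to the non-evaluable label is most likely to apply in the case of progression. Its example has a baseline sum of 50 mm and two of three lesions later totalling 80 mm, a rise of 30/50 = 60%, above the 20% threshold whatever the third lesion measures. That scan would satisfy route b). This stands and narrows the gap to scans whose readable lesions do not settle the matter; with 50 mm as reference, those whose measured lesions total less than 50 × 1.2 = 60 mm.

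**The loss is not always final.** A later progression re-enters through a) or b), and death remains an event. A timepoint with no imaging is not a performed assessment, so route a) still applies. All of this stands.

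**This is a derivation detail for the SAP.** An SAP could define a subsequent assessment as an evaluable one. But 10.4 is not silent: it states a complete rule with a closing sentence for all remaining patients, and that rule gives the wrong answer here.

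**Stronger readings that the documents do not support.** A reader might infer that shrinkage on the next drug can cancel a progression, since Section 3.1.1 says patients on new therapy "should be followed according to the protocol schedule until there is confirmed disease progression". That sentence concerns patients who start new therapy without having progressed. After progression, the same section provides for survival and subsequent-therapy follow-up; with no further scan, route a) counts the progression.

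A reader might also infer from Section 3.5.1, which lists ir-RECIST PFS beside RECIST v1.1 PFS, that the primary test is exposed. Section 3.5.1 does not call it primary, Section 10.2.2 lists it as secondary, and Section 10.2.1 has no confirmation step. Nor does each affected patient add a full patient to an 8-month rate: row 4 shows why not under Kaplan-Meier.

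**Conclusion.** The point holds as a gap in a stated rule for a secondary endpoint. Read literally, Section 10.4 drops or postpones an ir-RECIST progression when the next scan was performed but cannot be evaluated, although the progression would stand had no scan been done. PFS in the affected patients is biased upward: by 8 weeks of added progression-free follow-up and loss of the event, or by a 16-week delay, in the examples. These sizes depend on the assumed 8-week grid.

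The overall size cannot be given. The protocol states no rate of non-evaluable scans, and only patients rescanned after a first progression are exposed. The primary 8-month PFS as defined in Section 10.2.1 and PFS by RECIST v1.1 are unaffected. Setting aside a progression that an evaluable scan fails to confirm is intended and is not criticised here.

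**What to change.** In Section 10.4, define the subsequent tumor assessment in both a) and b) as the next evaluable assessment at least 4 weeks after the criteria were first met, the interval in Appendix II. State that a non-evaluable scan is treated as no subsequent assessment. The event then stands at the date first met unless the next evaluable assessment fails to confirm it. Censor patients without progression at the last evaluable assessment, and align Section 10.9.

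The cost is a sentence or two in the protocol and a small change to the derivation program. ir-RECIST PFS may be slightly less favourable, and an occasional pseudo-progression followed only by unreadable scans will count as an event, as one followed by no scan already does.
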